3.1 Primary Objective

Aim 1 will test if African ancestry (%AF) is associated with short SWS duration and poor SWA in older AAs. **Challenge:** AAs consistently spend less time in SWS than whites²³⁻³². Although SWS shows significant heritability, social stressors may moderate these differences. **Approach:** test whether %AF⁴⁰ is associated with SWS characteristics after controlling for psychosocial factors (*e.g.* stress related to ethnicity). **Outcome:** positive results would suggest that racial differences in SWS have genetic underpinnings.

Aim 2 will test the effect of race and its interaction with baseline short SWS duration/poor SWA on longitudinal amyloid deposition. **Challenge:** AAs spend less time in SWS²³⁻³², a sleep stage important for A β dynamics⁴¹⁻⁴³ that may confer protection against amyloid deposition⁴⁴. **Approach:** assess how race is associated with longitudinal PiB uptake and its interaction with short SWS duration and poor SWA, after controlling for: 1) medial prefrontal (mPFC) atrophy, TST, AHI4% and cerebrovascular damage (measured as white matter lesion [WML] volume and abnormal diffusion kurtosis imaging [DKI] indices); and, 2) psychosocial factors, health care behaviors and medical morbidity. **Outcome:** reduced SWS/SWA would become a novel risk factor for AD in African Americans (AAs).

Aim 3 will test the effect of race and baseline poor SWA on cognition. **Challenge:** race and poor sleep have been associated with cognitive impairment. However, most studies are confounded by the inclusion of OSA patients, subjective measurements of sleep, lack of valid cognitive assessments for AAs and inadequate enrollment of minorities. **Approach:** we will test for the association between race and longitudinal changes in global cognition, memory, executive function and a sleep-dependent spatial navigational memory task. In addition, we will test their interaction with baseline SWA, using a similar approach as in Aim 2. **Outcome:** positive results would emphasize the importance of health messages promoting good sleep hygiene among AA elderly.

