3.2 Secondary Objectives (if applicable)

Secondary Objective : **Exploratory:** we will test whether loss of sleep-dependent spatial navigational memory at baseline is a predictor of cognitive decline at follow-up. A **linked objective** is to identify how the relationship between SWS/SWA and the rate of change in PiB uptake might be confounded by mPFC atrophy (for measures of SWS) and DWML volumes and DKI (for measures of PiB uptake).

4 Study Enrollment and Withdrawal

Subjects:

210 cognitively normal, ages 60-75, self-identified as African-American (150) or non-Hispanic white

CONFIDENTIAL

This material is the property of the NYU School of Medicine and Langone Medical Center. Do not disclose or use except as authorized in writing by the study sponsor

(60), Clinical Dementia Rating (CDR) of 0, ≥ -1.25 in global cognition z-scores from the WHICAP battery adjusted for race and education, English speakers, and with enough literacy to provide voluntary consent will be invited to participate.

Exclusion criteria at enrollment will be: intention to move from NYC within the same year, irregular sleep-wake cycles defined as ‘ ≥ 3 sleep episodes per 24-hr period’ or ‘day to day irregularity greater than 90 min. based on actigraphy, less than 5 or more than 10 hours of TST; OSA (defined as $AHI_4\% > 15$ and $AHI_4\% > 5$ with $Epworth \geq 10$); neurodegenerative disorders, history of early onset familial AD; insulin dependent diabetes; bipolar disorder, schizophrenia, intellectual disability or substance abuse; non-controlled pulmonary or cardiac diseases; brain tumors; stroke; head trauma and hydrocephalus.

Lifelong depression and anxiety will be allowed as long as there has been no active depressive episode within the last two years. Current use of any sedative/hypnotics or stimulants, gabapentin, pregabalin, tricyclic antidepressants, and trazodone or other psychoactive medications that may alter SWS. Stable (3 months or longer) use of antidepressants will be allowed. Caribbean or African-born blacks or subjects that don't fulfill inclusion criteria but express interest will be offered participation in similar NYU NIH-funded studies on sleep or normal aging.

Study Enrollment:

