6.1 Procedures/Evaluations

Clinical evaluation: all subjects will perform a standardized clinical evaluation (UDS 3.0) given to all participants seen at the NYU ADC. The purpose of this clinical evaluation is to establish that subjects are cognitively normal, identify concurrent medications that may act as confounders (*e.g.*, benzodiazepines, trazodone, suvorexant), increase reproducibility of the clinical evaluation, and facilitate collaborative research with NACC (see *Resource Sharing Plan*). Depressive symptoms will be measured using the Geriatric Depression Scale (GDS)^{212;213}. We will add information about: health insurance, annual household income, perceived discrimination (Index of Race-Related Stress [IRRS]-Brief Version B²¹⁴), the Weinstein Noise Sensitivity Scale (WNSS)²¹⁵, the Perceived Stress Scale (PSS)²¹⁶ and the SF36 health behaviors survey²¹⁷ to control for environmental, health and psychosocial factors that might disrupt sleep. In addition, all subjects will undergo complete fasting blood tests (CBC with differential and platelet count, highly sensitive CRP, ESR, total T₃ and T₄^{*}, lipid profile, RPR^{*}, comprehensive metabolic profile with insulin, folate^{*}, homocysteine^{*}, and vitamin B₁₂^{*}, SMA-18, HbA_{1c}, hemogram)). Subjects will then complete the WHICAP battery and the AMNART test⁴. The tests comprising this neuropsychological battery were chosen because unlike the UDS 3.0, they have race-specific norms⁵. We will construct three composite scores for general cognition, memory, and executive function from factor analyses. We will use total recall, delayed recall, and delayed recognition from the Buschke Selective Reminding Test²¹⁸ to construct the memory composite. The executive functioning composite will be created using the Color Trail-Making Test (A and B)²¹⁹, WAIS-R (Wechsler Adult Intelligence Scale-Revised), Similarities, Identities/Oddities subtest of the Mattis Dementia Rating Scale²²⁰, two cancellation tasks and semantic fluency for animals²²¹. All of the above variables, together with phonemic fluency²²¹, the 15-item Boston Naming Test²²², repetition task (high-frequency phrases of the Boston Diagnostic Aphasia Examination[BDAE]²²³; and a comprehension task, will contribute to the composite for general cognition. Means and standard deviations (SD) will be calculated from baseline scores for non-demented WHICAP subjects controlling for age, race and years of education using robust norms. Z-scores for each of the cognitive measures will be averaged to create a composite z-score for each of the three domains. Only subjects diagnosed as cognitively normal with a z-score >-1.25 SD of the mean in general cognition will be invited to participate. The time to complete the WHICAP test battery will range from 45-90 min. On visit 2, prior to the PET/MR scan, subjects will complete the UDS 3.0 cognitive evaluation to facilitate collaborative research with NACC.

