9.1 Study Hypotheses

1. Hypothesis 1.1: poor SWS characteristics (short SWS duration, low %SWS, low relative SWA, low SWS continuity and high AI) at baseline will be associated with high %AF. Hypothesis 1.2: psychosocial factors (*e.g.* perceived discrimination) will partially moderate the above relationships.
2. Hypothesis 2.1: race will be associated with longitudinal increases in the annual rate of AD_{PiB}mask change. Hypothesis 2.2: the effect of race in terms of longitudinal increases in AD_{PiB}mask will be partially explained by poor relative SWA at baseline.
3. Hypothesis 3.1: race will be associated with longitudinal changes in global cognition, memory, executive function and sleep-dependent spatial navigational memory. Hypothesis 3.2: the association of race in terms of cognitive decline will be partially explained by poor relative SWA at baseline. Exploratory Hypothesis: absence of improvement in sleep dependent memory consolidation at baseline will be associated with longitudinal decreases in global cognition, memory and executive function.

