linear regression, with rate of change of AD_{PiB}mask as the dependent variable and race as independent, adjusting for the matching factors: age, sex, BMI, education and annual income (block 1); ApoE4 and ABCA7 (block 2); DWML volumes, DKI indices and mPFC volume (block 3); and SWS characteristic (*e.g.* relative SWA) (block 4). Other covariates (*e.g.*, psychosocial) will be included in the final models if significantly different between AAs and whites as indicated by unequal variance t tests. Although we anticipate that relative SWA will be the best predictor of longitudinal change in AD_{PiB}mask, the best fitting model will be then replicated with each of the other SWS characteristics not listed before. On a final step, we will test whether the effect of SWS on amyloid deposition is different (*i.e.*, stronger) among AAs. The model would include AD_{PiB}mask change, the binary indicator of race (AA=1 *vs.* white=0) and SWA as described in H1.2. If the interaction is significant, it will imply that the effect of SWA on amyloid varies as a function of race. The sign of the estimated coefficient for this term would indicate whether SWA has a significantly stronger or weaker effect among AA. Exploratory Hypothesis: cognitive z-score change in subjects that show improvement in maze CT will be compared with those that don't show improvement using ANCOVA controlling for age, sex, BMI, race, education and ApoE4 status.

- **Post-hoc analyses**: a subset of *post-hoc* analyses will be performed by controlling by PiB levels at baseline and by splitting the sample into PiB+ and PiB- at baseline and performing a separate analysis for each subset. Stratified analyses will also be performed for men and women, as well as for AAs and whites. In addition, we will formally test the impact of PiB status (defined as PiB SUVR \geq 1.4) on the association of sleep measures with longitudinal increases in AD_{PiB}mask. Although we do not anticipate that sleep or SWS characteristics will change over the follow-up period, *post-hoc* analyses will be performed by assessing longitudinal changes in the sleep measures as correlates and predictors of longitudinal changes in the outcomes measures, using paired sample t-tests to assess the change in outcomes and sleep.

10 Source Documents and Access to Source Data/Documents

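### The exploratory maze ANCOVA analyses cognitive change without the baseline cognitive score, so it cannot separate lost sleep-dependent memory from starting cognition

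*Combined protocol and SAP*

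**What the plan says.** The exploratory hypothesis in section 9.1 is that "absence of improvement in sleep dependent memory consolidation at baseline will be associated with longitudinal decreases in global cognition, memory and executive function". Section 3.2 states the aim as prediction: "we will test whether loss of sleep-dependent spatial navigational memory at baseline is a predictor of cognitive decline at follow-up".

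The analysis is in section 9.3, which sets participants with overnight maze improvement against those without it. The method and covariates are given in these words: "don't show improvement using ANCOVA controlling for age, sex, BMI, race, education and ApoE4 status". The outcome is a change score with six named covariates, none of them cognitive.

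The missing covariate is collected. Section 5.2 places the WHICAP battery at baseline Visit 1, before the polysomnography nights and the maze, and again at 30 months. Section 6.1 builds the composites: "Z-scores for each of the cognitive measures will be averaged to create a composite z-score for each of the three domains". They are normed for age, race and education, and entry requires a general-cognition z-score above about -1.25 (sections 4.1 and 6.1).

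For Aim 3, section 3.1 says only that "we will test their interaction with baseline SWA, using a similar approach as in Aim 2". Section 9.3 treats Hypotheses 2 and 3 together. Its blocks hold demographic and socioeconomic factors, two genes, MRI measures and a slow-wave-sleep measure, with no baseline cognition. The post-hoc paragraph adds control for baseline PiB, which is amyloid.

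**The concern.** Whether the maze improves overnight is something participants bring with them. Starting cognition may plausibly relate both to that and to the rate of later decline, and nothing in the design balances it. The entry floor narrows the range of starting cognition but leaves a spread.

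The intended claim is that lost overnight consolidation carries information about future decline. Without the baseline composite in any written version of this analysis, a reader of a positive result could not rule out that the two maze groups simply began at different cognitive levels. The same question arises for slow wave activity (SWA) in Aim 3, if those models use the Aim 2 blocks as written.

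**Working it through.** **1. The plan's own figure.** Section 9.2 gives 80% power for a sleep measure explaining 3% of the variance in change, after covariates explaining 25%, with 200 complete participants. For one added predictor, f² = 0.03/(1 - 0.25 - 0.03) = 0.0417 and the noncentrality is 200 × 0.0417 = 8.33. With a 5% F test and 12 covariates (assumed; 5 to 15 makes no material difference), power is 0.819. The figure reproduces. It concerns Aims 2 and 3; no power is stated for the maze ANCOVA.

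**2. Simulation of the maze comparison.** From the plan: n = 200, significance at 5% (taken as two-sided), outcome = change, two maze groups. Assumed, because the documents give no values:
- true baseline C ~ N(0,1);
- a latent maze score with correlation r to C, split at its median;
- true follow-up = C + bC + N(0, 0.5²), so b is the extra decline in SD per SD of lower starting cognition;
- observed scores with reliability 0.8 or 0.9;
- no true maze effect.

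The six covariates are not simulated, so r and b stand for what remains after them. False-positive rates (%):

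| Reliability | r | b | Planned (change only) | Baseline-adjusted only | Both required |
|---|---|---|---|---|---|
| 0.9 | 0.2 | 0.15 | 7.3 | 6.2 | 5.6 |
| 0.9 | 0.3 | 0.30 | 27.6 | 8.8 | 8.2 |
| 0.9 | 0.4 | 0.30 | 43.4 | 13.4 | 13.2 |
| 0.9 | 0.4 | 0 | 5.0 | 10.4 | 2.6 |
| 0.8 | 0.2 | 0.15 | 7.0 | 9.4 | 6.5 |
| 0.8 | 0.4 | 0.15 | 11.9 | 23.5 | 11.7 |
| 0.8 | 0.4 | 0.30 | 31.4 | 26.6 | 24.8 |
| 0.8 | 0.4 | 0 | 4.8 | 19.6 | 2.6 |

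Repeat runs of the worst row (reliability 0.9, r = 0.4, b = 0.30) gave 43-45% for the planned test and 12-14% when both models were required.

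**3. Entry floor.** Admitting only z > -1.25 lowers the planned test's rate in that row to about 33-34%, against about 14% with both required. At reliability 0.8, r = 0.4, b = 0, the rates become 6.0% planned and 5.4% both, so the rule adds little there.

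**4. The opposite direction.** If maze status depends on the observed baseline score, regression to the mean makes low starters appear to decline less. With reliability 0.7-0.9, the floor and no true effect, the planned model is biased by +0.03 to +0.15 SD. It then falsely shows less decline in non-improvers in 6-26% of trials, against a nominal 2.5% in that direction. Baseline adjustment removes this bias.

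**5. Power.** With a true effect of 0.3 SD and r = 0, planned versus both required is 87.1% versus 86.1% at reliability 0.9, and 68.1% versus 65.5% at 0.8. The loss is 1.0 and 2.6 points.

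**The case against.** For non-randomised groups, a change score and a baseline-adjusted change answer different questions, and neither is simply the correct one. This stands. With b = 0 the planned test holds its size, and adding an error-prone baseline creates false positives. A reader might infer that the plan will report lower starting cognition as a sleep-memory effect, or that adjustment alone is the cure. The documents support neither: the first needs lower starters to decline faster, for which they give no figure, and the second fails in the b = 0 rows.

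A reader might also infer that the plan forgoes power. With equal variances and baseline-follow-up correlation ρ, adjustment multiplies the residual variance by (1 - ρ²)/(2(1 - ρ)) = (1 + ρ)/2. That would lift 82% to 91%, 88% or 86% at ρ = 0.5, 0.7 or 0.8, but only if the adjusted model decided alone. A rule that also requires the planned test cannot exceed the planned test's power.

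In some settings the adjusted model is far stronger: 95% against 63% under the two-model rule, with a true effect of 0.3 SD, r = 0.3, b = -0.15 and reliability 0.9. The planned model alone also has 63% there, so nothing is lost against the plan.

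The Aim 3 part is inference, since no Aim 3 covariate list is written. Section 9.3 lets other covariates into the final models if African American and white participants differ on them, so baseline cognition could enter that way. That clause depends on race differences, not maze status, and does not reach the maze ANCOVA, which has its own list.

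Finally, the maze analysis is labelled exploratory, and entry also requires CDR 0 and MoCA above 25. Both limit what is at stake.

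**Conclusion.** The omission is in the text, and the maze ANCOVA as written cannot separate loss of sleep-dependent memory from starting cognition. The documents do not settle the direction or size of any bias. Under the assumed ranges (r 0.2-0.4, b 0.15-0.30, reliability 0.8-0.9) the planned test is falsely positive in about 7-45% of trials without the entry floor and 7-34% with it. If decline does not depend on starting level, and maze status follows true rather than observed baseline, it stays near 5%.

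Requiring agreement of two models helps unevenly: from up to 45% down to about 14% at reliability 0.9, but only from about 30% to 22-27% at 0.8. For Aim 3 the point is conditional on those models following the Aim 2 blocks, and the simulated figures do not cover continuous SWA. The change is worth making before analysis, but the point does not threaten the amyloid endpoint.

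**What to change.** In section 9.3:
- Keep the planned change model and add beside it the same model with the baseline value of the same composite.
- State that maze improvement will be described as a predictor of decline beyond starting cognition only if the association is significant in the same direction in both.
- State whether the Aim 3 SWA models follow the Aim 2 blocks; if they do, apply the same pair of models there.
- Note that residual bias remains because the baseline score is measured with error, and claim no gain in power.

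The rule cannot add false claims relative to the plan, because every claim must still pass the planned test. The cost is a few lines of SAP text, one covariate already collected at Visit 1, and about 0-3 points of power in the simulated settings. No new data or participants are needed.

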9.2 Sample Size Determination

Power was assessed under the assumption that dropout replacement will allow complete data to be acquired from 200 subjects. Based on the existing literature²³⁻³², the coefficient of variation (CV) of SWS duration is anticipated to be as high as 90% among AA and 40% among whites. Baseline data from 150 AA and 60 whites will therefore provide 80% power at the 5% significance level to detect a mean SWS duration among whites that is at least 28% higher than among AA. Based on PD4, the CV of PiB uptake at baseline is anticipated to be as high as 35% among AA and 25% among whites, providing 80(90)% power at the 5% significance level to detect a mean PiB uptake among AAs that is at least 13%(15%) higher than in whites. For Aim 1, the study will have 80% power at the 5% significance level to detect correlations of magnitude $|r|=0.20$ (the study from Halder et al³⁹ showed an R^2 of 11, implying an even greater correlation of 0.33 can be expected in our study). The multivariable regression analysis will have 80% power to detect SWS characteristics that can explain 3% of the variance in the longitudinal change in AD_{PiB}mask (Aim 2) or cognition (Aim 3) after adjusting for covariates that together explain at least 25% of the variance in AD_{PiB}mask/cognition. The detectable effect of 3% variance explained, implies the study can detect partial correlations of magnitude 0.1 between SWS and the outcomes adjusted for the cofactors. It is noted that the power of the multivariable analyses will improve if the covariates explain >25% of the variance. The study will have 80% power to detect sleep measures that explain 10% of the variance in the AD_{PiB}mask ratio even if the covariates explain a negligible percentage of the variance.

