9.3 Statistical Methods

General considerations: we will incorporate standard techniques such as omnibus tests and appropriate adjustments to significance (α) levels (*e.g.*, Bonferroni correction) for *post-hoc* contrasts to control for multiple comparisons. Both selection and attrition biases might occur. Appropriate techniques (*e.g.*, Heckman 2-stage approach (GEE Probit Model)^{254;255} and Monte Carlo (EM algorithm)²⁵⁶ will be used to address biases or missing data. Attributes of those who withdrew to follow-up will be contrasted with completers to determine sources of attrition biases. Since only two time points will be analyzed, we will use linear regression models with the annual rate of amyloid change as dependent variable. Significance will be defined by $p < .05$ where p will be Bonferroni corrected when testing *post-hoc* contrasts.

- **Hypothesis (1)**: H1.1) for %AF associations, linear regression models, with each of SWS characteristics as the dependent variable, will be regressed on %AF controlling for age, sex, BMI, AHI, TST, sleep efficiency and WASO. H1.2) This model will test interaction by including the best SWS predictor as dependent variable, the psychosocial factor as a classification factor, %AF and the term created as the cross product of psychosocial factors and %AF.
- **Hypothesis 2-3 (H2-3)**: First we will calculate the associations between race and AD_{PiB}mask represented both as binary (AA *vs.* white) and numeric (%AF). Further analyses will use the representation (s) of race significantly associated with amyloid burden. Second, we will use hierarchical

CONFIDENTIAL

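### Sex as an effect modifier is addressed only by separate post-hoc fits in men and women; unlike race and PiB status, it has no test of the difference

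*Combined protocol and SAP*

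**What the plan says.** The post-hoc paragraph of 9.3 lists three splits of the sample: PiB-positive against PiB-negative at baseline, men against women, and AAs against whites. The last two come in one sentence: "Stratified analyses will also be performed for men and women, as well as for AAs and whites".

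Two of the three splits are backed by a test of whether the association differs between the groups:

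- **Race.** The last step for Hypotheses 2-3 fits a race x SWA term and says how to read it: "If the interaction is significant, it will imply that the effect of SWA on amyloid varies as a function of race".
- **PiB status.** The post-hoc paragraph says "we will formally test the impact of PiB status" on the association of sleep measures with AD_PiBmask increase. Cognition is not mentioned there.
- **Sex.** Nothing comparable is given. Elsewhere in 9.3 sex is an adjusting covariate: in H1.1 ("controlling for age, sex, BMI, AHI, TST, sleep efficiency and WASO"), in the Aim 2-3 model ("adjusting for the matching factors: age, sex, BMI, education and annual income (block 1") and in the exploratory ANCOVA.

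The multiplicity rule is "Significance will be defined by $p < .05$ where p will be Bonferroni corrected when testing *post-hoc* contrasts".

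**The concern.** A p-value from the fit in men tests whether there is an association in men, and the p-value from the fit in women does the same for women. Neither tests whether the two slopes differ. The analysis as written therefore yields no valid test of a sex difference. The authors use cross-product terms for this kind of question elsewhere (H1.2 and race x SWA), so the omission for sex is a gap by the plan's own standard.

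Each sex has roughly half the sample. At an effect the whole study can just detect, each half is close to a coin toss for significance, so one sex will often be significant and the other not when the true slopes are identical. If that pattern were reported as a sex-specific effect of slow wave sleep on amyloid, no test of the difference would stand behind it.

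**Working it through.** **Inputs**

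- N: "complete data to be acquired from 200 subjects" (9.2).
- Effect: "The multivariable regression analysis will have 80% power to detect SWS characteristics that can explain 3% of the variance in the longitudinal change", with covariates explaining 25% (9.2).
- Alpha 0.05 (9.3). Sidedness is not stated; two-sided is assumed.
- Sex split: not stated. Section 4 balances sex between the race groups but fixes no male-to-female ratio. Assumed range: 100/100 to 130/70.
- Covariates: 8 assumed. Any number from 0 to 15 leaves the results unchanged to within about 0.2 points.

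**1. Reproduce the plan's power.** Use the noncentral F test of one added predictor with noncentrality N x f2.

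f2 = 0.03 / (1 - 0.25 - 0.03) = 0.0417; N x f2 = 200 x 0.0417 = 8.33; power = 81.9%.

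With f2 = 0.03 / 0.75 = 0.04, power is 80.3%. Both agree with the stated 80%.

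**2. Power within each sex, same true effect in both.** For n = 100 the noncentrality is 100 x 0.0417 = 4.17. The chance that exactly one sex is significant is D = p1(1 - p2) + p2(1 - p1).

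| Men/women (either order) | p1 | p2 | D at alpha 0.05 | D at alpha 0.025 per stratum |
|---|---|---|---|---|
| 100/100 | 52.4% | 52.4% | 2 x 0.524 x 0.476 = 49.9% | 48.4% |
| 120/80 | 60.1% | 43.7% | 0.601 x 0.563 + 0.437 x 0.399 = 51.3% | 49.6% |
| 130/70 | 63.6% | 39.0% | 0.636 x 0.610 + 0.390 x 0.364 = 53.0% | 51.1% |

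The last column applies if the Bonferroni rule is taken to cover the two strata. It hardly changes the result.

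A simulation of 40,000 studies at 100/100 gave 50.2% with one sex significant, 26.7% with both and 23.2% with neither. The interaction test rejected in 5.0% of the same studies.

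**3. Vary the effect size, at 100/100 and alpha 0.05.**

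| True effect, equal in both sexes | Power per sex | D |
|---|---|---|
| None | 5% | 2 x 0.05 x 0.95 = 9.5% |
| 1% of variance (covariates 25%) | 21.0% | 33% |
| 3% of variance (covariates 25%) | 52.4% | 49.9% |
| 10% of variance, negligible covariates (9.2) | 91.0% | 16-17% |
| r = 0.33 (9.2, expected for Aim 1) | 92-93% | 12-14% |

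For equal strata D = 2p(1 - p), which cannot exceed 50% and reaches it at p = 50%. The 3% row is therefore almost exactly the maximum for an even split. The ranges in the last two rows reflect the choice of test (noncentral F or Fisher z) and rounding. Aim 1 concerns AAs only; with 75 AAs per sex and r = 0.33, Fisher z gives 82.9% power per sex and D = 28%.

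**4. Power of the interaction test.** At 80% overall power the standardised effect is 1.960 + 0.842 = 2.802. With two equal halves each slope has twice the variance of the pooled slope, so their difference has four times the variance and twice the standard error. A sex difference as large as the overall detectable effect then has standardised size 2.802 / 2 = 1.401. Power = Phi(1.401 - 1.960) = Phi(-0.559) = 28.8%.

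**The case against.** The best defence is that the error is not in the text. No aim or hypothesis concerns a sex difference, 9.3 does not say the two fits will be compared, and the analyses are labelled post-hoc. Separate fits can simply report sex-specific estimates. The paragraph also does not say which association (race or sleep) is to be stratified. All of this stands. A reader might infer that the plan will declare sex differences by setting one p-value against the other; the documents do not say so.

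A reader might also infer that equal effects would look different about half the time whatever their size. That is not supported. Section 9.2 presents 3% of variance as what the study can detect, not as what it expects, and the discordance is much lower at the larger effects 9.2 mentions and under no effect.

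Two further limits stand. Sex is not ignored elsewhere, since it is adjusted for in every main model and balanced between race groups; the gap concerns effect modification alone. And the formal PiB-status test covers amyloid change, so it is no precedent for the cognition models.

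The Bonferroni rule is not an answer. It lowers the threshold within each stratum (discordance under no effect becomes 2 x 0.025 x 0.975 = 4.9%) but supplies no test of the difference. Low power of the interaction is also no reason to omit it: the stratified fits hold no more information about the difference, and the interval shows how little there is.

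**Conclusion.** The concern holds in a limited form. For sex as an effect modifier, 9.3 offers only separate fits, and these give no valid test of a difference. With 200 complete subjects, two-sided 0.05 and an equal true effect near the plan's detectable size, exactly one sex would be significant in about 50-53% of studies for splits from 100/100 to 130/70, or about 48-51% at 0.025 per stratum. The sex split is an assumption, and so is the effect size, which matters more. An interaction test would reject 5% of the time in the same setting.

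No primary or secondary conclusion depends on this. It is a cheap improvement to one post-hoc item.

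**What to change.** In the post-hoc paragraph of 9.3:

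- Say which association is stratified by sex.
- Add a sex x SWS-characteristic term to the pooled AD_PiBmask-change model, and to the cognition models if they too are to be stratified by sex.
- Report the difference in slopes with its 95% CI.
- State that any statement about a sex difference rests on this term, and that the separate fits in men and women are descriptive.

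The cost is a sentence or two of text and one extra model term, with no new data or visits. The downside is power of about 29% at a 50:50 split for a difference as large as the overall detectable effect. The result should therefore be reported as an estimate with its interval, and a non-significant term should not be read as showing that men and women do not differ.

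### The only method named for relating change in sleep to change in outcomes is the paired t-test, which cannot show association; no model in Section 9.3 fills the gap

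*Combined protocol and SAP*

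**What the plan says.** The last sentence of the post-hoc paragraph in Section 9.3 has three parts.

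- **Expectation:** "we do not anticipate that sleep or SWS characteristics will change over the follow-up period".
- **Question:** the analysis will proceed by "assessing longitudinal changes in the sleep measures as correlates and predictors of longitudinal changes in the outcomes measures".
- **Method:** this will be done "using paired sample t-tests to assess the change in outcomes and sleep".

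Elsewhere in 9.3 the named tool for amyloid is regression. The general considerations state that, with two time points, "we will use linear regression models with the annual rate of amyloid change as dependent variable". The model for Hypotheses 2 and 3 is a hierarchical "linear regression, with rate of change of AD_{PiB}mask as the dependent variable and race as independent", with a slow wave sleep (SWS) characteristic entered in block 4. Section 3.1 (Aims 2 and 3) and Hypotheses 2.2 and 3.2 in Section 9.1 tie that sleep term to baseline. Significance is set at 0.05, with Bonferroni correction for post-hoc contrasts.

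**The concern.** The question is about association: do people whose sleep changed more also show more amyloid or cognitive change? The method attached to it is about means: did average sleep, or the average outcome, move between baseline and follow-up? These are different estimands, and an answer to the second says nothing about the first.

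The plan's own expectation sharpens the mismatch. If mean sleep is not expected to change, the expected paired t result for sleep is null. Individual changes could still vary widely around a zero mean and track the outcomes closely, and the named test would not detect it. Conversely, a cohort in which both means drift with age would give two significant t-tests with no link between the changes.

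At stake is the one analysis in 9.3 that uses follow-up sleep measures. Without a model fixed in advance, the outcome form, the sleep measures and the adjustment set would all be chosen after the data are seen.

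**Working it through.** The plan gives no sample size, power or effect size for this analysis, so there is no figure to reproduce. The check is by formula and by simulation.

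**Inputs from the plan.** Section 9.2 assumes that "dropout replacement will allow complete data to be acquired from 200 subjects", so n = 200. Alpha is 0.05 (Section 9.3). Sidedness is not stated, and two-sided is assumed.

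**Inputs assumed.** The two changes are bivariate normal with SD 1. Mean changes are 0 or 0.2 SD. The correlation rho between sleep change and outcome change is 0, 0.2, 0.5 or 0.9. There are 4,000 replicates per setting.

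**Step 1, what each statistic contains.** For one variable with within-person change d, the paired statistic is t = mean(d) / (SD(d) / √n). It uses one variable at a time. The slope of outcome change on sleep change is cov(Δsleep, Δoutcome) / var(Δsleep). Only the second involves the association.

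**Step 2, rejection rates at n = 200.**

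| Mean change, sleep / outcome (SD) | rho | Paired t, sleep | Paired t, outcome | Regression slope |
|---|---|---|---|---|
| 0 / 0 | 0 | 5.2% | 5.6% | 4.4% |
| 0 / 0 | 0.2 | 5.0% | 5.0% | 81.4% |
| 0 / 0 | 0.9 | 5.0% | 5.1% | 100% |
| 0 / 0.2 | 0 | 4.9% | 80.6% | 4.8% |
| 0 / 0.2 | 0.9 | 5.0% | 81.1% | 100% |
| 0.2 / 0.2 | 0 | 79.4% | 80.6% | 4.6% |
| 0.2 / 0.2 | 0.2 | 80.0% | 80.6% | 81.0% |
| 0.2 / 0.2 | 0.9 | 81.8% | 81.3% | 100% |

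The rows for rho = 0.5, and for 0 / 0.2 at rho = 0.2, show the same pattern. The paired t columns move with the means and not with rho. The slope column moves with rho and not with the means. The 0 / 0.2 rows match the plan's expectation of stable sleep: the sleep t-test stays near 5% even at a correlation of 0.9.

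**Step 3, power of the missing analysis, as an illustration.** By Fisher z, power = Φ(atanh(r)·√(n − 3) − z). With r = 0.20 and n = 200, atanh(0.20) = 0.2027, √197 = 14.04, and the product is 2.85.

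- At two-sided alpha 0.05: 2.85 − 1.96 = 0.89, giving 81.2%.
- At alpha 0.01, which is 0.05 / 5 for the five sleep measures in Hypothesis 1.1 (the choice of family is an assumption): 2.85 − 2.58 = 0.27, giving about 61%.

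**Step 4, search for a model elsewhere.** The general regression sentence in 9.3 names amyloid change as the dependent variable, does not mention cognition, and names no sleep-change regressor. The Hypothesis 2–3 model enters race and an SWS characteristic, which the aims and hypotheses place at baseline. The exploratory ANCOVA compares groups defined by maze improvement. None enters change in sleep.

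**The case against.** The strongest reply is textual. The final clause gives the t-tests a limited object, namely change in the outcomes and change in sleep. That is a proper use, and it fits the sentence's opening, since a paired t-test checks whether sleep was in fact stable. The language of correlates and predictors points to regression, which is the default in 9.3 for amyloid change, so an analyst would probably supply it.

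This reading is fair, and a reader should not infer that the plan certainly misuses the t-test. But on this reading the association question has no stated model at all. The default does not close the gap: it covers amyloid only, while the sentence speaks of outcomes in the plural and Aim 3 concerns cognition. The correction needed is the same on either reading.

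Three stronger inferences are tempting, and the documents do not support them.

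- **That the second round of polysomnography would be wasted.** Follow-up night 2 is also the sleep interval between maze training and testing (follow-up visits in Section 5.2, maze description in Section 6.1), and change in that task is an Aim 3 outcome. The documents do not say that change-on-change analysis is why the nights were scheduled.
- **That two mean changes would be reported as evidence of association.** The sentence leaves room for that, but nothing in the plan says it will happen.
- **That the replacement analysis would have 80% power.** The |r| = 0.20 in Section 9.2 is stated for Aim 1. The 81% above is for one unadjusted test. Bonferroni correction would lower it, and so would measurement error in the change scores.

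**Conclusion.** The point holds. The one method named in the sentence cannot answer the question the sentence poses, and no model elsewhere in 9.3 does so. This follows from the form of the statistic and does not depend on the simulation settings, which only illustrate it.

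Its weight is modest. This is one clause in a post-hoc paragraph; the primary amyloid model, the sample size and alpha are unaffected. The power figures (about 81% at alpha 0.05, about 61% at 0.01) assume 200 complete pairs, a true correlation of 0.20, a two-sided test, no covariates and, for the second, a family of five sleep measures. They show that a regression is feasible at this sample size and are not a claim about the power of the adjusted analysis.

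**What to change.** Replace the method clause of the post-hoc sentence in Section 9.3 with two statements:

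1. Paired t-tests will describe the mean change in each sleep measure and each outcome.
2. The association will be tested by linear regression of the annual rate of change in the amyloid index, and separately of each cognitive outcome, on annual change in relative SWA and in each other SWS measure. Each model will adjust for the baseline value of that sleep measure, race and the Hypothesis 2–3 covariates, with the plan's Bonferroni correction across sleep measures.

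Race should be named explicitly, because in the main model it is the independent variable and not one of the block 1 matching factors. The plan should also state the Bonferroni family. Because both changes are measured over the same interval, the result should be reported as concurrent association and not as evidence of which change came first.

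The cost is a short edit to the analysis plan. It needs no new visits or measurements, since baseline and follow-up polysomnography, PiB PET and cognitive testing are already scheduled.
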